8. STUDY ASSESSMENTS AND PROCEDURES

Overview

The [Schedules of Activities](#) summarize the frequency and timing of all measurements applicable to this study.

Up to Amendment 7, all participants will be provided access to an eCOA digital tool. This eCOA will be used to collect COVID-19 signs and symptoms surveillance info for all participants, ePRO (Symptoms of infection with Coronavirus-19 [SIC], including body temperature, and pulse

oximetry results) for all participants at baseline and in case of COVID-19-like signs and symptoms, and e-Diary data on 7-day reactogenicity (solicited signs and symptoms, including body temperature) in the Safety Subset. All eCOA assessments should be conducted/completed before any tests, procedures, or other consultations to prevent influencing participant responses. Refer to the PRO completion guidelines for instructions on the administration of ePROs. The baseline SIC must be completed prior to the first vaccine administration.

As of Amendment 7, the number of on-site visits for participants who are not part of the Immunogenicity Subset is reduced. For these participants, any outstanding on-site visits will be replaced by phone call visits. No further booster vaccination will be provided in the protocol. In addition, requirements for COVID-19 episodes reporting are changed (ie, a passive follow-up approach is adopted, defined as safety follow-up phone call visits by the site instead of on-site study visits to document COVID-19 events as SAEs, AEs, or MAAEs until end of study). All participants will be reconsented at an unscheduled visit and as per local informed consent process guidelines.

If multiple assessments are scheduled for the same timepoint, it is recommended that procedures be performed in the following sequence: vital signs before blood draws. If needed, assessments may be performed on another day within the applicable visit window. Actual dates and times of assessments will be recorded in the source document, the eCRF, or the sample requisition form.

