8.1.3. Efficacy Assessments

Up to Amendment 7, identification and molecular confirmation of SARS-CoV-2 infection and symptomatic COVID-19 will be performed throughout the study as described in Section 8.1.2. Up to Amendment 7, the ePRO to evaluate VE parameters will be the SIC. See Section 8.1.3.1 for Case Definition of Moderate to Severe/Critical COVID-19 and Section 8.1.3.2 for Case Definition of Mild COVID-19. Molecular confirmation of SARS-CoV-2 infection by a central laboratory will be used for the analysis of the case definition. As of Amendment 7, no identification or molecular confirmation of SARS-CoV-2 infection and symptomatic COVID-19 will be done via central testing.

COVID-19 cases will be assessed independently by a Clinical Severity Adjudication Committee (see Section 8.1.3.6). Classification of severity will be based on the highest degree of severity during the observation period (see Sections 8.1.3.1, 8.1.3.2, and 8.1.3.4) and on the Committee's clinical judgement.

Up to Amendment 7, the occurrence of COVID-19-related hospitalization and COVID-19-related complications (such as but not limited to hyperinflammatory syndrome, pneumonia, neurological or vascular complications, severe pneumonia, severe neurological or vascular events, acute respiratory distress syndrome, renal complications, sepsis, septic shock, death)⁷¹ will be monitored throughout the study.

As a secondary objective, VE in the prevention of asymptomatic SARS-CoV-2 infection and mild COVID-19 will be analyzed. For samples collected prior to implementation of Amendment 7: an immunologic test for SARS-CoV-2 seroconversion (ELISA and/or SARS-CoV-2 immunoglobulin assay) based on SARS-CoV-2 N protein, may be performed to identify cases of asymptomatic infection. This assay will be performed on samples obtained at Day 1 (before the 1st vaccination) and 14 days, 6 months, and 1 year after the second vaccination (see Section 8.1.3.5). Additionally, this assay will be performed on blood samples obtained (prior to Amendment 7) at the unblinding visit (before open-label vaccination) and at the Booster Vaccination Visit (before booster vaccination).

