8.1.3.5. SARS-CoV-2 Seroconversion Assessment

For samples collected prior to implementation of Amendment 7, an immunologic test for SARS-CoV-2 seroconversion (ELISA and/or SARS-CoV-2 immunoglobulin assay) based on SARS-CoV-2 N protein, may be performed to identify cases of asymptomatic infection on samples obtained at Day 1 (before the 1st vaccination) and 14 days, 6 months, and 1 year after the second vaccination (see Section 8.1.4) and at the unblinding visit and at the Booster Vaccination Visit.

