The aim is to recruit up to 6,000 participants in the Safety Subset. At the time of writing the Protocol Amendment 4, the target recruitment has not been completed yet. Every effort will be made to reach the target of 6,000 participants, but the final number of participants recruited in the Safety Subset may be less due to unblinding of the participants. After an individual participant has been unblinded, he/she is no longer considered as part of the Safety Subset and no further solicited/unsolicited symptoms that are specific to the Safety Subset will be collected. All other safety reporting requirements applicable for all participants will be maintained (Section [8.3.1](#)).

As of Amendment 7, a passive follow-up approach is adopted: follow-up visits or phone calls by the site at scheduled time points to collect information on any protocol-required safety assessment (see Section [8.3.1](#)).

In addition, SAEs, AEs, and MAAEs related to COVID-19 need to be reported together with the concomitant medications related to these events until study end. Any confirmatory COVID-19 laboratory information should be reported in the eCRF.

Populations for Analysis Sets

For purposes of analysis, the following populations are defined:

Full Analysis Set (FAS): All randomized participants with at least 1 documented study vaccine administration, regardless of the occurrence of protocol deviations and serostatus at enrollment. Analyses of safety will be performed on the FAS. Vaccine efficacy analyses can be repeated using the FAS.

Safety Subset: subset of the FAS for the analysis of solicited and unsolicited AEs.

Per-protocol Efficacy (PP) population^a: Participants in the FAS who receive 2 doses of study vaccine and who are seronegative at the time of 1st vaccination and at Day 71, and who have no other major protocol deviations that were judged to possibly impact the efficacy of the vaccine before unblinding. The PA of VE will be based on the PP population. In the double-blind phase, the PP will be the main analysis population for efficacy analyses.

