Per-protocol Immunogenicity (PPI) population^a: All randomized participants who receive 2 doses of study vaccine in the double-blind phase, including those who are part of the Immunogenicity Subset and for whom immunogenicity data are available, excluding participants with major protocol deviations expected to impact the immunogenicity outcomes. In addition, for participants who experience a SARS-CoV-2 event (molecularly confirmed), samples taken after the event and samples taken outside protocol windows will not be taken into account in the assessment of the immunogenicity. The PPI population is the primary immunogenicity population. For key tables, sensitivity immunogenicity analyses will also be performed on the FAS, including participants who are part of the Immunogenicity Subset for whom immunogenicity measures are available. Excluded samples might be taken into account as well in the sensitivity analysis. Analyses of vaccine immunogenicity and immune correlates of risk will be based on PPI.

The populations for the open-label active and open-label passive follow-up phase are described in the SAP.

The list of major protocol deviations to be excluded from the efficacy for the double-blind analysis and/or immunogenicity analyses will be specified in the SAP and/or this list will be reported into protocol deviation dataset of the clinical database before database lock and unblinding.

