9.4. Efficacy Analyses

The SAP for the primary analysis was finalized prior to database lock and it includes a more technical and detailed description of the statistical analyses described in this section. This section is a summary of the planned statistical analyses of the most important endpoints including primary and key secondary endpoints.

^a If a participant would be vaccinated out of window due to a study pause or any other reason, this will not by default be a reason for excluding this participant from the PP and PPI population. A sensitivity analysis might also be performed. Further details will be described in the SAP. This analysis set will only be applied to the double-blind phase.

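### In the double-blind phase, the per-protocol immunogenicity set drops post-infection samples only after a molecularly confirmed event, so infections known only from N-serology still count as vaccine antibody response

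*Protocol*

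**What the plan says.** The PPI definition is under Populations for Analysis Sets, which follows protocol Section 9.2.4. The set takes randomized participants with two doses in the double-blind phase and available immunogenicity data, "excluding participants with major protocol deviations expected to impact the immunogenicity outcomes". At sample level it disregards out-of-window samples and, "for participants who experience a SARS-CoV-2 event (molecularly confirmed), samples taken after the event". It sets no condition on serostatus at baseline or later. The role of the set is explicit: "Analyses of vaccine immunogenicity and immune correlates of risk will be based on PPI". A sensitivity analysis on the full analysis set (FAS) is planned for key tables and may bring excluded samples back. The footnote to both per-protocol sets adds: "This analysis set will only be applied to the double-blind phase".

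The per-protocol efficacy (PP) set, defined just before, requires participants "who are seronegative at the time of 1st vaccination and at Day 71". Section 8.1.3.4 classifies a participant without qualifying symptoms as having asymptomatic or undetected COVID-19 on either a positive molecular test or a positive non-S serology. Sections 8.1.3 and 8.1.3.5 foresee N-based testing at Day 1, at 14 days, 6 months and 1 year after the second dose, and at the unblinding visit. Section 9.4.2 uses the available N-ELISA results to count infections for efficacy at the primary analysis.

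**The concern.** The vaccine encodes the S protein, so N-serology separates infection from vaccination; a footnote to Section 8.1.4 relies on this when it steers outside testing to nucleocapsid assays. A participant who seroconverts to N has been infected and may carry S-binding antibody from that infection. The PPI rule does not see this unless a molecular test was also positive. The same Day 71 serum can then remove a participant from the PP set as seropositive while its S-antibody value counts in the PPI as response to vaccine.

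Two outputs are exposed. One is the descriptive geometric means, on which Section 9.2.2 relies for the size and time course of the humoral response. In vaccinees the error runs upward, and it grows with each visit as undetected infections accumulate. The other is the correlates work. Section 9.2.3 draws its controls from vaccine recipients who were not infected, and the PPI is its base. A vaccinee with an undetected infection could enter as an uninfected control with a raised antibody level.

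**Working it through.** **Step 1. Compare the rules on one participant.** Take a vaccinee who is N-negative at Day 1, N-positive at Day 71, and never positive on a molecular test.

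| Provision | Treatment |
|---|---|
| Asymptomatic case definition (8.1.3.4) | Infected, on serology alone |
| PP efficacy set | Excluded, not seronegative at Day 71 |
| Efficacy against any infection (9.4.2) | N-ELISA result enters the infection endpoint |
| PPI set | Retained, Day 71 and later double-blind samples included |

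A participant who is N-positive at Day 1 is likewise excluded from PP and retained in PPI.

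**Step 2. Look for another provision that removes these samples.** The deviation clause excludes whole participants for major protocol deviations. Infection is not ordinarily a deviation, and the need here is to drop samples from a date onward. The FAS sensitivity analysis is wider than the PPI and may add samples, so it cannot remove contamination. Section 9.5.1 explores baseline factors, which could cover entry serostatus but not later seroconversion. Fold rise from baseline does not help for seroconverters, because their baseline was taken before infection.

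**Step 3. Size.** The protocol states no figure to reproduce. Let *s* be the share of retained active-group samples from unrecognised infections and *f* the fold rise in S-antibody they carry. The mean log titre moves from μ to (1 − s)μ + s(μ + log f) = μ + s·log f, so the geometric mean is multiplied by f^s. Both *s* and *f* are assumptions.

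| s | f = 2 | f = 5 | f = 10 | f = 20 | Participants in a cell of 50 |
|---|---|---|---|---|---|
| 2% | 1.01 | 1.03 | 1.05 | 1.06 | 1 |
| 5% | 1.04 | 1.08 | 1.12 | 1.16 | 2.5 |
| 10% | 1.07 | 1.17 | 1.26 | 1.35 | 5 |

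The cell of 50 is one active group in Table 3. The only related figure in the protocol is the 10% seroprevalence assumed in Section 9.2.1. Applied to entry serostatus, it gives 0.10 × 50 = 5 baseline-seropositive participants per cell.

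**Step 4. Compare with sampling error.** With an assumed log10 standard deviation of 0.4 to 0.5 and n = 50, the 95% confidence factor is 10^(1.96 × 0.4/√50) = 1.29 to 10^(1.96 × 0.5/√50) = 1.38. At s = 5% the inflation (1.04 to 1.16) lies inside it. At s = 10% and f = 20 the inflation of 1.35 is about as large as the interval's half-width.

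**The case against.** The best defence is that immunogenicity is descriptive with no hypothesis test (Sections 9.5 and 9.5.1), that the double-blind window limits how many undetected infections can build up, and that the likely inflation is within sampling error for a cell of 50. Keeping baseline seropositives in a descriptive set can be a deliberate choice. Correlates methods go to a separate plan, and Section 9.2.3 already separates N-seropositive from N-seronegative placebo participants. The Amendment 6 rationale cites this study's primary analysis, so redefining the primary set now would be post hoc.

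These points lower the weight of the finding and shape the remedy. They do not make the rule sound. The protocol fixes the trigger itself, and fixes it more narrowly than its own definition of infection. The N-seropositive and N-seronegative split in Section 9.2.3 concerns placebo participants, not vaccinated controls.

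A reader might infer more from Amendment 7. From then on N-testing is specified "For samples collected prior to implementation of Amendment 7, an immunologic test for SARS-CoV-2 seroconversion", and "As of Amendment 7, no identification or molecular confirmation of SARS-CoV-2 infection and symptomatic COVID-19 will be done via central testing". Only visits outside the subset are cut back ("the number of on-site visits for participants who are not part of the Immunogenicity Subset is reduced"), and the subset schedule in Section 8.1.4 runs to 18 months and 2 years. The tempting conclusion is that late PPI samples carry infection-raised antibody that nobody can identify. The documents do not support it. The PPI is confined to the double-blind phase, which under Section 9.4.1 ends for each participant at the unblinding visit. Amendment 7 follows Amendment 6 of 15 October 2021, which already placed boosters in the open-label phase. Open-label populations are left to the statistical analysis plan. Available local or self-reported confirmations are still recorded after Amendment 7 (Sections 8.1.2.1 and 8.3.1).

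**Conclusion.** The point holds for the double-blind PPI. As written, the rule counts antibody raised by infection as vaccine response for two groups: baseline N-seropositives, and N-seroconverters without a positive molecular test. No other stated provision clearly removes them. Under the assumed shares and fold rises, inflation of the geometric mean runs from about 1.01 to 1.35 times. It is small if undetected infection was rare and visible if it reached about one sample in ten. The protocol supplies neither input, so this is an illustrative range and not an estimate.

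The Amendment 7 testing changes are not a fault of this rule. At most they are a limitation of the open-label data: study-run N-testing and central molecular testing are not planned for samples collected after that amendment.

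**What to change.** Extend the PPI sentence so that samples from the first N-seropositive result onward are also not taken into account, alongside those after a molecularly confirmed event. Summarise participants who are N-seropositive at baseline separately. Keep all excluded samples in the FAS sensitivity analysis. If the primary immunogenicity analysis has already been run, leave its population as it was and present the new rule as a labelled supplementary analysis, so that no primary set is redefined after unblinding.

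The cost is low. Day 1 and Day 71 serology is already needed to define the PP set, and later double-blind N results are already foreseen. The downside is slightly fewer samples per timepoint. A small gap remains: an infection between N-tested visits is dated only to the next positive sample, so a subset sample drawn in between could still be retained. For the open-label report, one sentence stating the post-Amendment 7 testing limitation is enough.

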9.3. Participant Information

For all participants, descriptive statistics of demographic (eg, gender, age, height, weight, BMI, race, and other baseline characteristics) will be provided by vaccination group. Additional characteristics related to current work situation, living situation, and community interactions will be collected for risk factor analysis, if allowed per local regulations. Risk factor data initially collected at screening from the participants, prior to implementation of the Protocol Amendment 2 will also be used for the planned risk-factor analysis. See also Section 9.4.3.

9.4. Efficacy Analyses

The SAP for the primary analysis was finalized prior to database lock and it includes a more technical and detailed description of the statistical analyses described in this section. This section is a summary of the planned statistical analyses of the most important endpoints including primary and key secondary endpoints.

^a If a participant would be vaccinated out of window due to a study pause or any other reason, this will not by default be a reason for excluding this participant from the PP and PPI population. A sensitivity analysis might also be performed. Further details will be described in the SAP. This analysis set will only be applied to the double-blind phase.

9.4.1. Primary Endpoint Evaluation for the Double-blind Phase

The double-blind phase of the study is designed to test the primary hypothesis of VE in the PP population: H0: VE $\leq 30\%$ versus H1: VE $> 30\%$ and will be evaluated at a 2.5% 1-sided significance level.

The primary endpoint will evaluate the first occurrence of molecularly confirmed, moderate to severe/critical COVID-19 according to the case definition in Section 8.1.3.1, with onset at least 14 days after the second vaccination (Day 71) with Ad26.COV2.S versus placebo, in the PP population, including all events from both age groups, with and without comorbidities.

Participants included in the seronegative analysis set are those participants with a negative SARS-CoV-2 serology test result at baseline.

The unblinding visit marks for a participant the end of the double-blind phase, and the start of the open-label phase. For a given participant, all data up to the unblinding visit will be incorporated in the analysis of the double-blind phase.

The minimum criteria that may trigger the primary analysis before at least 90% of participants are unblinded is if the prespecified harm boundaries have been crossed.

A successful primary efficacy conclusion will require establishing the hypothesis H1: VE $> 30\%$ for the primary endpoint.

Exact Poisson regression will be used to estimate the VE and associated CI taking into account the follow-up time. To evaluate the primary null hypothesis: H0: VE $\leq 30\%$ versus H1: VE $> 30\%$ for the primary endpoint, 95% 2-sided confidence interval based on Poisson regression model will be used.

The decision rules for harm are detailed in Section 9.4.1.1.

For any case definition to be considered for classification of COVID-19 cases, there needs to be at least one SARS-CoV-2 positive RT-PCR or molecular test result from any available respiratory tract sample (eg, nasal swab sample, sputum sample, throat swab sample, saliva sample) that is confirmed by the central laboratory. It is possible that not all samples can be confirmed at the time of the analysis. Hence, a sensitivity analysis may be performed using all RT-PCR or molecular test result, regardless of the confirmation by the central laboratory.

The primary efficacy analysis will pool data across populations (with and without comorbidities) to evaluate the primary and secondary objectives. In addition, these will be supplemented with a subgroup analysis for age and comorbidities employing a descriptive summary including 95% confidence intervals to describe the VE in each subpopulation.

In addition, to assess potential time-effects of VE, the Kaplan-Meier method will be used to plot the estimated cumulative incidence rates over time for the vaccine and placebo groups. This

method will be used to estimate cumulative VE over time, defined as $[(1 \text{ minus ratio (vaccine/placebo) of cumulative incidence by time } t) \times 100\%]$.

Furthermore, VE will be evaluated in seronegative participants, counting primary endpoints since onset after the first vaccination.

Of note, the data may be pooled with data of other ongoing efficacy studies in support of health authorities' interactions.

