8.1. Efficacy and Immunogenicity Assessments

No generally accepted immunological correlate of protection has been demonstrated for SARS-CoV-2 to date.

8.1.1. Prespecified Criteria for Suspected COVID-19 Prior to Amendment 7

The criteria for suspected COVID-19 (ie, the triggers to proceed with home-collection of the nasal swabs on COVID-19 Day 1-2 and to proceed with the COVID-19 Day 3-5 visit) are prespecified as follows:

- **A positive RT-PCR result for SARS-CoV-2, through a private or public laboratory independent of the study, whether symptomatic or asymptomatic**

OR

- **New onset or worsening of any 1 of the symptoms listed below, which lasts for at least 24 hours, not otherwise explained:**

Headache

Malaise (appetite loss, generally unwell, fatigue, physical weakness)

Myalgia (muscle pain)

Chest congestion

Cough

Runny nose

Shortness of breath or difficulty breathing (resting or on exertion)

Sore throat

Wheezing

Eye irritation or discharge

Chills

Fever ($\geq 38.0^{\circ}\text{C}$ or $\geq 100.4^{\circ}\text{F}$)

Pulse oximetry value $\leq 95\%$, which is a decrease from baseline

Heart rate ≥ 90 beats/minute at rest, which is an increase from baseline

Gastrointestinal symptoms (diarrhea, vomiting, nausea, abdominal pain)

Neurologic symptoms (numbness, difficulty forming or understanding speech)

Red or bruised looking toes

Skin rash

- Taste loss or new/changing sense of smell
- Symptoms of blood clots: pain/cramping, swelling or redness in your legs/calves
- Confusion
- Bluish lips or face
- Clinical suspicion/judgement by investigator of symptoms suggestive for COVID-19

As several of the prespecified criteria for suspected COVID-19 overlap with vaccine-related reactogenicity, investigators' clinical judgement is required to exclude vaccine-related events when assessing suspected COVID-19.

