Testing done centrally	
 Nasal swab for virology testing (molecular confirmation of SARS-CoV-2 infection and viral load testing) 	
 At baseline/Visit 2/Day 1 (nasal swab collected by qualified study staff) At unblinding visit and at Booster Vaccination Visit for all participants On COVID 19 Day 1 2 (nasal swab collected by the participant at home)

Laboratory Assessments	Parameters	Timepoints
	
 Serum sample for sero confirmation of past SARS CoV 2 infection 	
 On COVID 19 Day 3 5 (nasal swab collected by qualified study staff) Once every 2 days following COVID 19 Day 3 5, until closure of the COVID 19 procedures (nasal swab collected by the participant at home)
	
 Nasal swab for virology testing (other respiratory pathogens using a broad respiratory pathogens panel) 	
 May be performed on samples collected during a confirmed COVID 19 episode and in a subset of samples from participants with a symptomatic infection. All participants during the open label phase.
	
 Saliva samples for virology testing (molecular confirmation of SARS CoV 2 infection and viral load testing) 	
 On COVID 19 Day 3 5 (saliva sample collected by the participant at the study site or at home) Once every 2 days following COVID 19 Day 3 5, until closure of the COVID 19 procedures (saliva sample collected by the participant at home)
	
 Serum samples for humoral immunogenicity 	
 In the double blind phase: Non Immunogenicity Subset: on study Visits 2 (baseline/Day 1), 5, 7, 8, and the early exit visit (if applicable). Immunogenicity Subset: on study Visits 2 (baseline/Day 1), 3, 4, 5, 7, 8, 9, 10, and the early exit visit (if applicable). Humoral immunogenicity samples may be used for N serology testing In the open-label phase: Visits 2 (baseline/Day 1), 5, 7, 8, and the early exit visit (if applicable) for both Immunogenicity and Non immunogenicity subsets.

Laboratory Assessments	Parameters	Timepoints

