8.1.3 Efficacy Assessments and related subsections 10.2 Clinical Laboratory Tests		
1.1 Synopsis 5.2 Exclusion Criteria	Clarification has been added that the history of Parkinson's disease, seizures, ischemic strokes, intracranial hemorrhage encephalopathy, meningoencephalitis is exclusionary from Stage 1.	Clarification.
5.2 Exclusion Criteria	It is clarified that participants with Guillain-Barré syndrome (Exclusion criterion 16) and participants requiring hospitalization as indicated in exclusion criterion 17 are excluded from the study altogether and not only in Stage 1 of the study.	Correction
5.1 Inclusion Criteria	Clarifications have been made to the inclusion criterion 4, indicating that Stage 1 participants can have a condition that is stable and well-controlled except the ones listed in exclusion criterion 14 which are associated with increased risk of progression to severe COVID-19. In addition, medication dose for allowed stable conditions (in all stages of the study) cannot have been increased within 12 weeks prior to vaccination.	Clarification
5.4 Screen Failures	It has been clarified that participants can be rescreened once, also when they meet all in- and exclusion criteria but the 28-day screening period was exceeded.	To allow participants who were found eligible to be enrolled in the study but were not randomized within the 28-day screening window to still participate in the study.
1.1 Synopsis 2.1 Study Rationale 4.1 Overall Study Design 9.8 Interim Analyses and Committees 10.3.6 Committees Structure	Reference to a possible sample size adjustment has been deleted and sample size considerations has been added.	Correction: per the VAC31518COV3009 Amendment 1, the sample size of approximately 30,000 participants was selected based on available epidemiology data at the time of Amendment 1 writing.
1.3.1 All Participants	It is clarified that the diagnostic molecular RT-PCR test for SARS-CoV-2 infection (from nasal swab taken at baseline) will be performed at a central laboratory on a retrospective basis. These baseline results are not available in real time, and thus cannot be used to inform participants at time of enrollment.	Clarification

Section number and Name	Description of Change	Brief Rationale

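### The seronegative set is fixed by baseline serology alone, so the vaccine efficacy estimate counted from the first dose includes infections already present on Day 1 and is pulled toward zero

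*Protocol*

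**What the plan says.** Three parts of the protocol bear on this.

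- **Set definition.** Section 9.4.1 states: "Participants included in the seronegative analysis set are those participants with a negative SARS-CoV-2 serology test result at baseline". No molecular result enters.
- **Use of the set.** Later in Section 9.4.1: "Furthermore, VE will be evaluated in seronegative participants, counting primary endpoints since onset after the first vaccination". This estimate supplements the primary analysis, and Section 9.4.1 attaches no hypothesis to it.
- **Available data.** Appendix 2 (Section 10.2) lists, among the centrally tested samples, a nasal swab for molecular confirmation of infection: "At baseline/Visit 2/Day 1 (nasal swab collected by qualified study staff)". No population or endpoint rule in the part of the protocol reviewed uses the result.

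The per-protocol (PP) population, under Populations for Analysis Sets after Section 9.2.4, is stricter. It needs two doses and covers participants "who are seronegative at the time of 1st vaccination and at Day 71, and who have no other major protocol deviations" judged to affect efficacy. The primary endpoint counts first moderate to severe/critical cases "with onset at least 14 days after the second vaccination (Day 71) with Ad26.COV2.S versus placebo, in the PP population".

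**The concern.** Antibodies appear some days after infection. Someone infected shortly before Day 1 can therefore be PCR-positive and seronegative on that day. Under the stated definition this person enters the seronegative set, and an illness starting soon afterwards counts as a case after the first vaccination.

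The vaccine had no chance to prevent that illness. Adding about the same number of such cases to each arm moves the ratio of the two rates toward one. The from-first-dose estimate then understates the protection it is meant to describe.

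The PP set has a much smaller gap of a similar kind. Serology on Day 71 can miss an infection acquired just before that day. A participant with a positive molecular test between dose 2 and Day 71 who has not seroconverted stays in the set.

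**Working it through.** **1. The plan's own figure.** Section 9.2.1 states that 104 events give about 90% power against H0: VE ≤ 30%, at VE 65%, one-sided 2.5% and 1:1 allocation. The vaccine share of events is 0.70/1.70 = 0.4118 under H0 and 0.35/1.35 = 0.2593 under H1. The exact binomial test rejects at 32 or fewer vaccine events of 104, with size 0.0187 and power 0.891. The figure is reproduced. At VE 65%, 104 events split into about 77 placebo and 27 vaccine.

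**2. Inputs for the from-first-dose estimate.**
- From Section 9.2.1: 15,000 per arm, 10% seroprevalence, so 15,000 × 0.90 = 13,500 seronegative per arm; VE 65%; annual incidence 1.4% (the timeline scenario) up to 4% (the upper end of the stated range).
- Assumed: follow-up T from dose 1 of 120 to 180 days; d = 3, 5 or 7 days' worth of cases already PCR-positive on Day 1 with onset afterwards; constant incidence; VE of 65% from dose 1, used as a reference value only.

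**3. Formula.** Placebo cases = 13,500 × i × T/365. Vaccine cases = 0.35 × placebo cases. Prevalent cases per arm = 13,500 × i × d/365. Arm size and incidence cancel:

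observed VE = 1 − (0.35T + d)/(T + d) = 0.65 × T/(T + d)

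| d (days) | T = 120 | T = 180 |
|---|---|---|
| 3 | 63.4% | 63.9% |
| 5 | 62.4% | 63.2% |
| 7 | 61.4% | 62.6% |

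At 1.4% incidence the prevalent cases number 13,500 × 0.014 × 3/365 = 1.6 to 13,500 × 0.014 × 7/365 = 3.6 per arm.

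**4. Cross-check by count.** Take 77 placebo and 27 vaccine cases as a base of realistic size. Adding b cases to each arm gives VE = 1 − (26.96 + b)/(77.04 + b): 64.2% for b = 1, 63.4% for 2, 61.0% for 5 and 57.5% for 10. The 1.6 to 3.6 cases from step 3 lie in the 61% to 64% part of this range.

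**5. Primary endpoint.** A Day 1 infection can enter only if the participant is still seronegative on Day 71 and then has a new qualifying onset. Assume 0.1% to 1% PCR-positive and seronegative on Day 1 (13.5 to 135 per arm), 10% of these still seronegative on Day 71, and 1% with a later event. That gives 13.5 × 0.1 × 0.01 = 0.01 to 135 × 0.1 × 0.01 = 0.14 events per arm. VE stays at 65%, and the 104 events and their power are unaffected.

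**The case against.** **Detail may sit in the SAP.** Section 9.4 calls itself a summary, and the list of excluding deviations is left to the SAP or the deviation dataset. The SAP and the first part of the protocol were not available for this review, so a PCR rule may exist there. That stands as a limit. But the set definition is stated, not deferred, and infection on Day 1 is not obviously a protocol deviation. If the SAP adds a PCR condition, the protocol sentence needs aligning with it.

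**Infected participants are removed anyway.** Section 7.1 withholds further doses after molecular confirmation on study samples, which takes a participant out of PP. It does not take anyone out of a set counted from the first dose.

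Three stronger readings are tempting but not supported.

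- *Prevalent infections bias the primary analysis.* A reader might compute the episodes starting in the 7 days before Day 71: 13,500 × 0.014 × 7/365 = 3.6 to 13,500 × 0.04 × 7/365 = 10.4 on placebo, and 0.35 times these, 1.3 to 3.6, on vaccine. Their onset is before Day 71, so the endpoint rule already excludes them. They do not measure carry-over.
- *Reactogenicity adds cases to the vaccine arm only.* Section 8.1.1 does say "As several of the prespecified criteria for suspected COVID-19 overlap with vaccine-related reactogenicity", but the sentence goes on to require investigator judgement to exclude vaccine-related events. Symptoms must last 24 hours and have no other explanation, and Section 8.1.3.6 makes the adjudicated severity definitive. Some asymmetry is possible, but reactions also occur on placebo and the protocol gives no rates to size it.
- *The dilution is much larger.* One could assume 0.3% PCR-positive on Day 1 (40.5 per arm) and two-symptom reactions in 30% of vaccine and 10% of placebo recipients, and reach 52% over 150 days at 1.4% incidence. No such rates are in the protocol. The 40.5 positives would be about half of all placebo cases in that period (13,500 × 0.014 × 150/365 = 77.7), and the scenario lets none of the safeguards above remove a case.

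**Conclusion.** The point holds for the supplementary estimate counted from the first vaccination. Followed as written, Section 9.4.1 counts infections already present on Day 1 as post-vaccination cases, although a centrally tested swab could identify many of them. The likely cost is about 1 to 4 percentage points of VE (65% read as 61% to 64%). This assumes 3 to 7 days' worth of prevalent cases, 120 to 180 days of follow-up, constant incidence and equal numbers in both arms. The direction does not depend on those values; the size does.

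For the primary endpoint, Day 1 infections have essentially no effect. The PP gap is limited to infections acquired shortly before Day 71 and is small. A Day 1 swab cannot detect those, so it needs its own condition.

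**What to change.** - **Section 9.4.1.** For the analysis counted from the first vaccination, define the set as seronegative at baseline and PCR-negative on the centrally tested Day 1 swab. Keep the serology-only set as a sensitivity analysis. Because this is a baseline condition, the comparison stays randomised.
- **PP definition.** Add a condition of no positive molecular SARS-CoV-2 test from Day 1 up to Day 71. This is a safeguard of small effect. It catches only infections that were swabbed and, like the Day 71 serology beside it, it is a post-randomisation exclusion.
- **SAP.** Use the same wording in both documents.

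The cost is one line in each of two definitions and slightly fewer participants and cases in the sets. The Day 1 swab is already planned and centrally tested, and swabs from suspected episodes are already collected under Section 8.1.2, so no new sampling is needed. The event target and the stated power do not change.
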